- Mean change from baseline in key SD-OCT parameters including CST, TMV, and parafoveal (inner ring of ETDRS grid) retinal thickness and the proportion of participants with ellipsoid or interdigitating zone disruption ([Table 5](#)). The difference in the proportion of participants with clinically significant ophthalmologic changes (as defined in the primary endpoint) between treatment group and the placebo group in each of SD-OCT parameters will be calculated. In addition, the change from baseline in individual SD-OCT and qFAF parameters listed in [Appendix 1](#) and [Appendix 2](#) will be tabulated and compared between tafenoquine and placebo-treated groups.
- Proportion of participants with abnormal changes from baseline observed on qFAF using the Spectralis HRA+OCT device with grey scale values extracted from these images for statistical analysis using qFAF software (Heidelberg Engineering).
- Mean change from baseline in BCVA. Changes from baseline in BCVA results by the ETDRS chart will be tabulated and compared between the two groups. A clinically significant deterioration is defined as a reduction of more than 4 letters from baseline (Week 1, Day 1 [Visit 2]) of 0.08 logMAR. The M-chart will be used to quantify the severity of the distortion (if detected). An additional analysis of BCVA changes will include the proportion of participants experiencing a 1-4 letter change (less than one line of ETDRS visual acuity change), a 5-9 letter change (1 line, but less than 2-line change), 10-14 letter change (2 lines, less than 3 lines) or 15 or more letter change (3 lines or more) in BCVA from baseline. A three line or more change in ETDRS BCVA at 4 meters is considered clinically significant.
- Proportion of participants with corneal deposits from slit lamp examination of the corneal epithelium. Severity of corneal deposits by impairment of vision: The proportion of participants with grades I to IV corneal deposits and with impairment on any of the vision tests will be tabulated for each time point for each eye and overall. For participants with corneal deposits identified from slit lamp examination, the time to first onset and time to resolution after treatment cessation will be tabulated. Corneal structural changes are defined as changes from Baseline (Week 1, Visit 2) of two or more grades of corneal changes. These data will also be provided in a listing.
- Time to onset and resolution of corneal deposits after treatment cessation.

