12.2.3.2. Secondary Endpoints

The incidence of AEs, SAEs, laboratory parameters and vital signs will be summarized descriptively by treatment group and study visit. The AEs will be summarized at $\geq 1\%$ (common) and $\geq 10\%$ (very common) level.

For the secondary safety endpoints, the proportion of participants with an abnormal change or new abnormal change will be compared by a Fisher's exact test between tafenoquine and placebo. The 95% CI of the abnormality rate will be summarized by Clopper Pearson Exact methodology. A logistic regression will be used to compare the risk of having the abnormality (odds ratio and 95% CI) between tafenoquine and placebo. These analysis methods will be applied to the following secondary safety endpoints: proportion of participants with abnormal changes from baseline observed on qFAF, proportion of participants with corneal deposits from slit lamp examination of the corneal epithelium, proportion of participants with new abnormal changes from baseline observed with color retinal digital photography (conventional and wide field), proportion of participants with new abnormal changes from baseline observed with microperimetry, proportion of participants with any new anomaly on the backlit ETDRS chart, proportion of participants with any clinically significant change in ETDRS BCVA (defined as ≥ 15 letter change [≥ 3 lines] of change in ETDRS BCVA at 4 meters), proportion of participants who develop a new color deficiency using the FM-100 hue test, proportion of participants who develop a loss of 0.12 or greater logCS on the Mars letter contrast sensitivity test, proportion of participants who develop a new identified psychiatric disorder, and proportion of participants with an AE of dizziness or vertigo and severity as assessed by the DHI.

For time to event safety endpoint, a log-rank test will be used to compare the time to onset/resolution of the event between tafenoquine and placebo. Cox regression will be used to compare the risk of having the safety endpoint (hazard ratio and 95% CI) between tafenoquine and placebo. The survival analysis methods will be applied to the endpoints of time to onset, and time to resolution of corneal deposits after treatment cessation.

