Change from baseline in BCVA, key SD-OCT continuous parameters, and LSEQ component scores will be analyzed by a random intercept mixed model to account for correlation between repeated measures. Treatment effect (difference and 95% CI) on the change from baseline variables will be estimated across study visits.

Specifically, the following assessments will be conducted for secondary safety endpoints, and the extra analyses, if mentioned as below, will be applied.

- Mean change from baseline in key SD-OCT parameters including CST, TMV volume, and parafoveal (inner ring of ETDRS grid) retinal thickness and the proportion of participants with ellipsoid or interdigitating zone disruption. The difference in the proportion of participants with clinically significant ophthalmologic changes (as defined in the primary endpoint) between treatment group and the placebo group will be calculated. In addition, the change from baseline in individual SD-OCT and qFAF parameters listed in [Appendix 1](#) and [Appendix 2](#) will be tabulated and compared between tafenoquine and placebo-treated groups.
- Proportion of participants with abnormal changes from baseline observed on qFAF using the Spectralis HRA+OCT device with grey scale values extracted from these images for statistical analysis using qFAF software (Heidelberg Engineering).
- Mean change from baseline in BCVA. Changes from baseline in BCVA results by the ETDRS chart will be tabulated and compared between the two groups. A clinically significant deterioration is defined as a reduction of more than 4 letters from baseline (Week 1, Day 1 [Visit 2]) of 0.08 logMAR. The M-chart will be used to quantify the severity of the distortion (if detected). An additional analysis of BCVA changes will include the proportion of participants experiencing a 1-4 letter change (less than one line of ETDRS visual acuity change), a 5-9 letter change (1 line, but less than 2-line change), 10-14 letter change (2 lines, less than 3 lines) or 15 or more letter change (3 lines or more) in BCVA from baseline. A ≥ 15 letter (≥ 3 line) or more change in ETDRS BCVA at 4 meters is considered clinically significant.

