- Proportion of participants with corneal deposits from slit lamp examination of the corneal epithelium. Severity of corneal deposits by impairment of vision: The proportion of participants with grades I to IV keratopathy (Orlando grading system for cornea Verticillata, a specific pattern of corneal deposits. For participants with corneal deposits identified from slit lamp examination, the time to first onset and time to resolution after treatment cessation will be tabulated. Corneal structural changes are defined as changes from Baseline (Week 1, Day 1 [Visit 2]) of two or more grades of corneal changes. These data will also be provided in a listing.
- Time to onset of corneal deposits and overall time duration to resolution post treatment start.
- Time duration to resolution of corneal deposits after treatment cessation.

- Proportion of participants with new abnormalities compared with baseline observed with color retinal digital photography (conventional and wide field);
- Proportion of participants with new abnormalities compared with baseline observed with microperimetry;
- Proportion of participants with any new anomaly on the backlit ETDRS chart;
- Proportion of participants who develop a new color deficiency using FM-100 hue test;
- Proportion of participants who develop a loss of 0.12 or greater logCS on the Mars letter contrast sensitivity test;
- Retinal changes (structural) and the impact on macular function (functional) will be tabulated for each time point for each eye. The macular function tests include BCVA (ETDRS), Color vision assessment with FM-100 hue test, M-chart, and microperimetry. Clinically significant changes in any of the five tests are will be counted as having an impact on macular function. Retinal abnormalities on funduscopy, digital fundus photography (conventional and wide field), SD-OCT and qFAF at Screening are considered to be structural changes but may not affect macular function with 12 months of treatment with tafenoquine.
- The proportion of participants with retinal abnormalities identified from digital photographs will be tabulated for each time point and overall. These data will also be provided in a listing;
- Proportion of participants who develop a new, current psychiatric disorder in accordance with the DSM-5 as assessed with the M.I.N.I 7.0.2 assessment questionnaire and suicidal ideation or suicide attempt by C-SSRS interview;

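### BCVA has two rules labelled clinically significant (a loss of more than 4 letters, or a change of 15 or more in either direction), and the macular-function table does not say which applies and names four of its five tests

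*Combined protocol and SAP*

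**What the plan says.** **BCVA rules.** The BCVA bullet in Section 12.2.3.2 states that "A clinically significant deterioration is defined as a reduction of more than 4 letters from baseline", equates 4 letters with 0.08 logMAR, and places the baseline at Week 1, Day 1 (Visit 2). It then lists bands of 1-4, 5-9, 10-14 and 15 or more letters, the last described as a "letter change (3 lines or more) in BCVA from baseline". It closes by saying that a 15-letter "or more change in ETDRS BCVA at 4 meters is considered clinically significant". The Synopsis (Statistical analysis) repeats the first rule and adds: "A three line or more change in ETDRS BCVA at 4 meters is considered clinically significant".

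**Named endpoint.** Section 12.2.3.2 lists the "proportion of participants with any clinically significant change in ETDRS BCVA", defined at 15 letters, among the proportions to be compared by Fisher's exact test, with Clopper-Pearson intervals and logistic regression. The Synopsis endpoints and Section 5.2.2 also list it.

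**Macular-function table.** Section 12.2.3.2 says: "The macular function tests include BCVA (ETDRS), Color vision assessment with FM-100 hue test, M-chart, and microperimetry". The next sentence begins: "Clinically significant changes in any of the five tests are will be counted as having an impact on macular function". The Synopsis has the same four tests and the same count of five. The table is per eye and per time point.

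**Baseline.** Section 8.1 takes the ophthalmic baseline from Screening. The schedule in Section 1 has ophthalmic tests at Screening and Weeks 12, 24, 52 and 64, and none at Visit 2.

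**The concern.** One bullet attaches the same label to two rules that differ threefold in letters and also in direction. The macular-function table uses that label as its counting criterion without choosing between them. Two programmers following the text could produce different BCVA counts from the same data, and they could not agree on which test is the fifth.

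The direction matters separately. The 15-letter endpoint is a safety endpoint, yet as written an improvement of 15 letters is an event. Elsewhere the plan states direction when it means loss: the Mars contrast endpoint is written as a loss, and item 2d of the ophthalmic AESI list in Section 10.11.1 is a reduction. Item 2e reverts to an undirected change.

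This table links structural retinal findings to visual function in an ophthalmic safety study. If its definition is left open, the choice could be made after the results are known.

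**Working it through.** **1. The plan's own units.** 0.08 logMAR / 4 letters = 0.02 logMAR per letter. More than 4 letters means at least 5 whole letters: 5 x 0.02 = 0.10 logMAR, or one line. Fifteen letters: 15 x 0.02 = 0.30 logMAR, or three lines. This agrees with the plan's bands, so the two rules really are one line and three lines.

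**2. How the rules classify an eye.**

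| Change from baseline | More-than-4-letter rule | 15-letter rule |
|---|---|---|
| Loss of 5 to 14 | significant | not significant |
| Loss of 15 or more | significant | significant |
| Gain of 15 or more | not significant | significant |

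The rules agree on large losses and disagree on moderate losses and large gains. The letter bands are also undirected and do not choose between the rules.

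**3. Count of tests.** Stated: five. Named: BCVA, FM-100, M-chart, microperimetry, which is four, in both Section 12.2.3.2 and the Synopsis. The stated count is not reproduced.

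**4. Baseline.** No BCVA is scheduled at Visit 2, so a Visit 2 baseline would have no scheduled measurement behind it. Screening, as in Section 8.1, is the only baseline that the schedule supplies.

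**5. Size.** The documents give no test-retest SD for BCVA. Assume no true change and a normal visit-minus-baseline difference with mean 0. SD 2 to 4 letters is the working range; SD 5 and 6 show sensitivity. With whole letters and a half-letter continuity correction, for one eye at one visit:

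- P(loss of 5 or more) = 1 - Phi(4.5/SD)
- P(loss of 15 or more) = 1 - Phi(14.5/SD)
- P(change of 15 or more, either way) = 2 x [1 - Phi(14.5/SD)]

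| SD | Loss of 5 or more | Loss of 15 or more | Change of 15 or more |
|---|---|---|---|
| 2 | 1.2% | below 0.001% | below 0.001% |
| 3 | 6.7% | below 0.001% | below 0.001% |
| 4 | 13.0% | 0.014% | 0.03% |
| 5 | 18.4% | 0.19% | 0.37% |
| 6 | 22.7% | 0.8% | 1.6% |

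With 300 participants per arm, one eye each at one visit, the smaller threshold flags about 300 x 0.012 = 4 to 300 x 0.130 = 39 eyes at SD 2 to 4. The 15-letter rule, counting both directions, flags fewer than one (300 x 0.00029 = 0.09 at SD 4). At SD 6 the figures are about 68 and 5.

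**The case against.** The best defence matches terms. The table counts *changes*, the named endpoint at 15 letters is also a *change*, and the more-than-4-letter rule is called a *deterioration*. On that reading the table uses 15 letters. This favours the larger threshold, and it means that the result is not wholly undetermined. But the text does not say so, the reading would count gains as an impact on macular function, and it leaves four against five unresolved.

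The defence is also right on scope. The table is not a listed secondary endpoint and is not among the Fisher-tested proportions; neither is the more-than-4-letter rule. BCVA is also analysed by a mixed model on change, by the 15-letter endpoint and by letter bands.

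Sections 12 and 12.2.1 leave detail to an SAP finalised before unblinding. That can supply missing detail, such as the numerical cut-offs that Section 12.2.3.2 does not give for FM-100, M-chart and microperimetry. It does not reconcile statements that conflict, and nothing in the supplied text does.

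Three stronger readings are tempting and not supported:

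- *That 9% to 67% of healthy participants would be flagged.* This takes any loss of 5 or more letters over 2 eyes and 4 visits as independent, at SD 2 to 4. The planned table is per eye and per time point, with no such roll-up. The visits of one eye also share a baseline, so independence fails; allowing for that (assumed correlation 0.5 between visits, eyes independent) gives roughly 8% to 54%. The per-eye, per-visit figures are the relevant ones.
- *That noise dominates the whole composite.* Only BCVA can be sized here; nothing comparable is available for the other tests.
- *That Mars contrast is the missing fifth test.* Neither list names it. Appendix 8 records that mfERG was removed from Section 12.2.3.2 in version 6.0, which suggests a count left over from that change. That is only a possible explanation; the finding rests on the current text.

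**Conclusion.** The point holds as a conflict in current wording. One label covers two BCVA rules, the macular-function table does not choose between them, its test count does not match its list, the named 15-letter endpoint counts gains as abnormalities, and the BCVA bullet cites a baseline visit without ophthalmic testing.

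Under the stated assumptions the choice of rule moves the no-effect flag rate for one eye at one visit from 1.2%-13% to at most about 0.014% for losses. At SD 6 the contrast is 22.7% against about 0.8%, so the 15-letter rule is not free of noise if variability is large. The gap between the rules remains wide across the range. The direction problem is one of meaning more than of frequency: by the same model a 15-letter gain by chance is as rare as a 15-letter loss.

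A reader might infer that the trial's main conclusion is affected. It is not. Table 5 defines the primary SOSE endpoint from SD-OCT and qFAF only, so that endpoint and its power do not involve BCVA, and the mixed model analyses letter change as a continuous variable. What is affected is the BCVA part of one descriptive table, and the direction of one tested secondary endpoint.

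**What to change.** 1. Reserve *clinically significant* for one BCVA definition in Section 12.2.3.2, the Synopsis, Section 5.2.2 and the macular-function table. The plan's own named endpoint, at 15 letters, is the consistent choice. This concerns analysis labelling and does not imply that smaller losses are harmless.
2. Keep the more-than-4-letter loss as a descriptive category under another label.
3. Write the 15-letter endpoint as a loss, tabulate gains separately, and split the letter bands by direction.
4. State that BCVA change is measured from Screening, and remove the reference to Visit 2 from the BCVA bullet.
5. Correct the count to the four tests named, or name the fifth explicitly.
6. Reconcile the wording of AESI items 2d and 2e in Section 10.11.1, since one gives a direction and the other does not.

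The cost is wording only: no new data, visits or sample size. Fewer participants will carry the label and the table will be less sensitive to small losses. The bands split by direction and the mixed model still show those.

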In Study 057, 10 (14.3%) participants in the tafenoquine Recommended Regimen group and 7 (21.9%) participants in the placebo group had evidence of corneal deposits in either eye at screening. After the screening visit, 15 (21.4%) participants receiving tafenoquine and 4 (12.5%) participants receiving placebo developed new-onset corneal deposits in one or both eyes during the study. Approximately 60% of the corneal deposit cases among participants receiving tafenoquine and 100% of the cases among participants receiving placebo emerged by Week 12 of the study. No trends were apparent with respect to the time to onset of these new corneal deposits in participants who did not have corneal abnormalities at screening. New-onset corneal deposits in all four participants in the placebo group resolved within 6 weeks of onset, while in the tafenoquine Recommended Regimen group, corneal deposits resolved within 12 weeks of onset in all but one participant. Corneal deposits in the remaining tafenoquine-treated participant resolved by Week 48.

In summary, benign, reversible corneal deposits have been noted in some participants treated with the tafenoquine Recommended Regimen. Participants are unaware of the development of these corneal deposits; it does not impact vision, and resolves within 1 year in all cases.

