The duration of subject's participation in the study will be up to 110 weeks, including a screening period of up to 6 weeks, a 52-week dosing period, and a 12-week follow-up period. If abnormalities are detected at the 12-week follow-up visit (Week 64 EOS) the subject will continue quarterly follow-up out to 12 months post last dose of IMP. For example, if corneal deposit was the only abnormality found during Week 64, then there is no need to repeat any of the ocular examinations except for corneal photography and corneal slit lamp examination at Weeks 76, 89 or 104 (Visits 8, 9 or 10).

The study will consist of the following for each participant:

- A screening period of up to 6 weeks prior to the first IMP dose. At the first screening visit (Visit 1a), subjects will be screened for eligibility with the exception of the

ophthalmologic assessments. If still eligible after the first visit, the subject will be scheduled for screening and baseline ophthalmic testing (Visit 1b).

- Randomization to receive tafenoquine or placebo in a 1:1 ratio using clinical site as a randomization variable;
- One 200 mg dose of tafenoquine per day for three consecutive days (loading doses; Days 1, 2 and 3) (Week 1, Visit 2) or equivalent dose of matched placebo;
- Once weekly 200 mg doses of tafenoquine or equivalent placebo on Week 2 through Week 52; Follow-up visits on Weeks 4, 12, 24, 52 and 64, and if applicable, Weeks 76, 89, and 104 to follow any ongoing AEs from the prior visit.

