9.2.6. Ophthalmic Assessments

The ophthalmic assessments will be conducted at Screening at (Visit 1b or 1a depending on site and subject preference) and repeated at Weeks 12, 24, and 52 of the Treatment Phase and at the EOS visit (Week 64). Ophthalmic assessments will be repeated at Week 76 (Visit 8) and quarterly thereafter to 12 months if ongoing or new ophthalmic abnormalities are identified at the Week 64 visit. Microperimetry testing will be conducted at Screening twice with the first result discarded to minimize learning effect and at Weeks 24, 52 and 64. Non-clinically significant abnormalities at Baseline (Week 1, Day 1) will be recorded as medical history and will only be followed up after Week 64 if the abnormality worsens during the Treatment Period.

Please note, only tests that are abnormal at the Week 64 visit will be followed up in Weeks 76, 89 or 104 (Visits 8, 9, or 10). For example, if corneal deposit was the only abnormality found during Week 64, then there is no need to repeat any of the ocular examinations except for corneal photography and corneal slit lamp examination at Weeks 76, 89 or 104. Therefore, not all ophthalmic testing will need to be completed in Phase 3 of the study at the discretion of the PI.

Specific test parameters will be provided in the ophthalmology manual for the study.

Routine ophthalmic tests will include the following:

- BCVA (ETDRS);
- Color vision assessment with FM-100 hue test. The Lanthony D15 test will be administered immediately prior to the FM-100 test to reduce learning affects.
- Mars letter contrast sensitivity test;
- M-chart;
- Slit lamp examination of anterior and posterior segment
- Intraocular pressure measurement
- Microperimetry (Weeks 24, 52 and 64).

- SD-OCT (including wide field macula scan);
- qFAF (set of 3 images to ensure consistency in measurement);
- Digital photograph of corneal surface (conventional and wide field); and,
- Digital photograph of retina (conventional and wide field)

Abnormal results may be further investigated using microperimetry, FM-100 hue test, Mars contrast sensitivity letter reading test, M-chart, slit lamp examination, SD-OCT (including wide field macula scan) and qFAF depending on the nature of the abnormality.

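### Corneal-deposit resolution is timed from the start or end of treatment, so no endpoint measures how long a deposit lasted, and deposits that clear during dosing have no valid after-cessation time

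*Combined protocol and SAP*

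**What the plan says.** The Synopsis, Section 5.2.2 and Section 12.2.3.2 carry the same two endpoints. The first is "Time to onset of corneal deposits and overall time duration to resolution post treatment start". The second is "Time duration to resolution of corneal deposits after treatment cessation". One resolution clock therefore starts at first dose and the other when treatment stops.

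On who is included, the Synopsis and Section 12.2.3.2 say that, for anyone in whom the slit lamp found a deposit, "the time to first onset and time to resolution after treatment cessation will be tabulated". Neither place requires the deposit to be present when treatment stops.

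On method, Section 12.2.3.2 prescribes a log-rank test and Cox regression for time-to-event endpoints and adds: "The survival analysis methods will be applied to the endpoints of time to onset, and time to resolution of corneal deposits after treatment cessation". The start-anchored resolution time is not named there.

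Dosing is described in Section 5.1 as "Once weekly 200 mg doses of tafenoquine or equivalent placebo on Week 2 through Week 52". Section 9.2.6 places the eye examinations at Weeks 12, 24, 52 and 64, with Weeks 76, 89 and 104 only for findings still being followed. Section 12 leaves detailed derivations to a later SAP. The supplied text gives no date formula and no rule for a deposit that clears before the last dose.

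**The concern.** How long deposits persist, and whether they reverse, are the main clinical questions about this known effect. Sections 2.1.1.1 and 2.3.2 rest on its being reversible. A time counted from first dose mixes when the deposit appeared with how long it stayed. Two participants with the same observed interval can differ widely, and two with very different intervals can tie.

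The after-cessation clock suits a reversibility question, but only for someone who still has a deposit when dosing ends. If a deposit has already cleared, the analyst must drop the participant, set the time to zero or redefine the risk set. These choices can give different results in the same log-rank or Cox analysis, and the plan does not choose. The problem is one of time origin and risk set, so methods for interval-censored data would not remove it.

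**Working it through.** The plan states no figure to reproduce, so the check applies its definitions to its own visit schedule.

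**Inputs.** O is the week a deposit is first seen and R the week of the first later examination without one, both on the eye-visit schedule (Section 9.2.6). C is the week of last dose, taken as 52 (Section 5.1).

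**Formulas.**
- Resolution from treatment start = R = O + (R − O)
- Resolution after cessation = R − C = R − 52
- Observed interval with a deposit = R − O

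| First seen (O) | First clear (R) | From start: R | After cessation: R − 52 | Observed interval: R − O |
|---|---|---|---|---|
| 12 | 24 | 24 | 24 − 52 = −28 | 12 |
| 24 | 52 | 52 | 52 − 52 = 0 | 28 |
| 12 | 64 | 64 | 64 − 52 = 12 | 52 |
| 52 | 64 | 64 | 64 − 52 = 12 | 12 |

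**Start-anchored time.** Rows 1 and 4 share a 12-week interval but score 24 and 64. Rows 3 and 4 both score 64, with intervals of 52 and 12. The excess over the observed interval is always O: 12, 24 or 52 weeks.

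**After-cessation time.** Rows 3 and 4 are usable. Row 1 has no valid value, and row 2 sits at about zero. With full dosing, 12/24 is the only pair of scheduled visits that gives a value below zero.

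**Can deposits clear on treatment?** Section 2.1.1.1 says so for Study 057, which dosed for about 24 weeks.
- Placebo: "100% of the cases among participants receiving placebo emerged by Week 12 of the study", and all cleared within 6 weeks of onset. Latest clearance is Week 12 + 6 = 18, which is 6 weeks before dosing ended.
- Tafenoquine: about 60% of 15 new cases (0.6 × 15 = 9) emerged by Week 12, and "corneal deposits resolved within 12 weeks of onset in all but one participant". A case that emerged by Week 12 and cleared within 12 weeks was gone by Week 24 at the latest.

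Study 033 points the other way: 69 of 74 participants on tafenoquine in the phospholipidosis subgroup had deposits at the end of prophylaxis, and 42 of the 69 had resolved 3 months later. On that pattern few deposits would clear during dosing.

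**The case against.** Several points on the other side stand.

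- **Sign.** A reader might infer that the derived times are negative in general. They are not. The start-anchored time is always positive. Only the after-cessation time can fall below zero, and even that follows from the endpoint wording, since no formula is given.
- **Transfer from Study 057.** A reader might also apply Study 057's counts here and conclude that most deposits would lack a valid time. The documents do not support that. This trial's first on-treatment eye examination is at Week 12. Section 2.1.1.2 gives Study 057 retinal examinations from Week 3. If its corneal examinations were similarly early, some deposits that emerged by Week 12 could have appeared and cleared before a Week 12 visit, and would never be recorded here. The text does not say how many were present at Week 12.
- **The cessation clock.** It is legitimate. Study 033 reported reversal on it, and the follow-up visits suit it. The phrase can also be read as covering only deposits present at cessation, and a SAP could say so.
- **Recoverability.** Onset and resolution share an origin, so duration follows by subtraction. The first endpoint's wording might even be meant as the duration of deposits arising after treatment start.
- **Visit spacing.** The observed interval is coarse. Seen at Week 12 and clear at Week 24 fits a true duration from just above 0 to 24 weeks. Clear at Week 24, seen at Week 52 and clear at Week 64 fits just above 0 to 64 − 24 = 40 weeks.

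These points narrow the concern without removing it. The subtraction is specified nowhere, and the tabulation sentence includes everyone with a deposit. A SAP that follows the endpoint wording would inherit both gaps.

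**Conclusion.** The concern holds in limited form. No endpoint is clearly timed from deposit onset to resolution, and the start-anchored time exceeds the observed interval by 12, 24 or 52 weeks depending on when the deposit is first seen. Separately, the after-cessation time sent to log-rank and Cox has no rule for deposits that clear during dosing. How many participants this affects cannot be derived from the documents, and the number may be near zero on the Study 033 pattern.

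The worked values assume that the last dose falls in Week 52 and that events are dated at nominal visits. Early discontinuation moves the cessation origin earlier, and unscheduled visits or the ±2-week windows could produce other values below zero. These are secondary safety endpoints for a finding the protocol regards as benign, so the change is worth making before unblinding but does not touch the primary analysis.

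**What to change.** Amend the Synopsis, Section 5.2.2, Section 12.2.3.2 and the SAP as follows.

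1. Replace the start-anchored resolution time with duration from the first examination showing a deposit to the first later examination showing none. Report it with the visit interval around each end, because scheduled eye visits are 12 to 28 weeks apart. Keep time to onset as its own endpoint.
2. Keep resolution after cessation, restricted to participants with a deposit at the last on-treatment examination, with time zero at the last dose.
3. Report separately, by arm, the proportion whose deposits cleared while on treatment.

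Slit lamp findings are already collected at every scheduled eye visit, so the cost is wording and programming. The drawback is a smaller denominator for the after-cessation analysis.
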